## Annex 2: Symptom Questionnaire

**Objective:** To correctly identify your genital discomfort (vagina and vulva). Please describe the discomfort caused by each of the following symptoms. If you do not have this complaint, please mark as "no discomfort".

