### **Project Objectives:**

**General Objective:** To determine the reliability, consistency, and validity of the psychometric properties of the Portuguese version of the DIVA questionnaire, adapted for our culture, in peri- and postmenopausal women. This validation will provide the foundation for using this questionnaire both in research and clinical practice with Portuguese women.

**Specific Objective:** To assess the discomfort of genital atrophy symptoms in the study participants and the impact of this problem on the quality of life of peri- and postmenopausal women in the Portuguese context.

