3. **DIVA Questionnaire (Day-to-day Impact of Vaginal Aging):** This questionnaire assesses the impact of vaginal aging on daily life. The original version was developed by Alison J. Huang (Annex 4), Director of the Department of Medicine at the University of California, San Francisco. It included 745 postmenopausal women, from 2008 to 2012, of multiethnic backgrounds with at least one complaint of genital atrophy (dryness, burning, irritation, and itching) or pain during sexual intercourse. The questionnaire is constructed with a multidimensional scale covering 4 domains: (1) daily activities, (2) emotional well-being, (3) sexual function, and (4) self-esteem and body image. The full version consists of 23 items, with a version for women without sexual activity that includes a "not applicable" option for the sexual function domain. The items are scored between 0 and 4, and the overall score is the average of the scores in each domain, with higher scores indicating a greater impact and severity of genital atrophy symptoms. The internal consistency of the original scale in English ranged from 0.47 to 0.72, with Cronbach's alpha between 0.82 and 0.93. Confirmatory factor analysis showed appropriate structural validity with a comparative fit index of 0.987 and a standardized root mean square residual (SRMR) of 0.038. A measurement property assessment of this symptom evaluation questionnaire identified it as one of the best quality and reliable tools for assessing female genital atrophy (Annex 1 and 4).
4. **EQ-5D** is a generic instrument for measuring health-related quality of life, which generates an index representing an individual's health state. Developed by the EuroQoL group since 1987 and made public in 1990, it is based on a classification system that describes health in five dimensions: mobility, self-care, usual activities, pain/discomfort, and anxiety/depression. Each dimension has three associated severity levels: no problems (level 1), some problems (level 2), and extreme problems (level 3) experienced by the individual. Another measure used is the EQ-VAS, a 20 cm vertical visual analog scale (VAS) ranging from 0 to 100, where 0 is the worst and 100 the best imaginable health. This measure of self-perceived health is

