### **Symptom Classification:**

- 1 - No Discomfort
- 2 - Mild Discomfort
- 3 - Moderate Discomfort
- 4 - Intense Discomfort

---

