#### **4. Vaginal or Vulvar Burning or After Sexual Intercourse**

- 1 No Discomfort
- 2 Mild Discomfort
- 3 Moderate Discomfort
- 4 Intense Discomfort

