#### **6. Pain During Sexual Intercourse**

- 1 No Discomfort
- 2 Mild Discomfort
- 3 Moderate Discomfort
- 4 Intense Discomfort

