#### **7. Bleeding or Unpleasant Odor During or After Sexual Intercourse**

- 1 No Discomfort

- 2 Mild Discomfort
- 3 Moderate Discomfort
- 4 Intense Discomfort

---

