**16. Current sexual activity:**

- Yes
- No

**Number of years without intercourse:** \_\_\_\_\_

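### Annex 2 items 6 and 7 give one code both to women who have no intercourse and to women whose intercourse is symptom-free, so discomfort on these items is probably understated for women exposed to intercourse

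*Protocol*

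**What the plan says.** Annex 2 lists seven symptoms. Each is answered on a printed scale from 1 (none) to "4 - Intense Discomfort". (Data Collection Instruments describes a five-point scale from 0 to 4 for this form. I use the printed annex; neither version has a not-applicable answer.) The opening instruction is "If you do not have this complaint, please mark as 'no discomfort". No recall period is given.

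Two items depend wholly on intercourse: item 6, "Pain During Sexual Intercourse", and item 7, "Bleeding or Unpleasant Odor During or After Sexual Intercourse". Items 4 and 5 mention intercourse but can also be answered without it; item 4 reads "Vaginal or Vulvar Burning or After Sexual Intercourse".

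The specific objective is "To assess the discomfort of genital atrophy symptoms in the study participants". Data Collection Instruments gives the Symptom Questionnaire a screening role, and Annex 2 says of itself that it is meant to identify genital discomfort correctly.

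The protocol expects women without sexual activity. The inclusion and exclusion criteria do not mention it. Data Collection Instruments describes DIVA "with a version for women without sexual activity that includes a 'not applicable' option for the sexual function domain". Annex 3 item 16 asks about current sexual activity and then for the "Number of years without intercourse".

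**The concern.** On items 6 and 7 the lowest code can mean that a woman has intercourse without the symptom, or that she has no intercourse and the symptom could not arise. The first is a result; the second is an absence of exposure. The form sets this by its instruction and its answer list.

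Annex 2 is the only form in the protocol that rates the intensity of discomfort symptom by symptom, so it is the natural source for the specific objective. If the two meanings are pooled, frequency and mean discomfort on items 6 and 7 are diluted by women who could not have the symptom. Some of these women may have stopped intercourse because it hurt, and for them a code of no discomfort would be furthest from their condition. A reader of the results could not tell a mild symptom burden from a large share of women without intercourse.

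**Working it through.** **Step 1. Compare the forms.** The protocol states no figure on this point to reproduce, so the first check is of the answer options.

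| Form | Items conditional on sexual activity | Separate answer for women without it | Recall period |
|---|---|---|---|
| Annex 1, Portuguese DIVA Part C | 10 to 18 | Yes, not applicable on every item | 4 weeks |
| Annex 6, FSFI-6 | 2, 3, 4 | Yes, code 0 for no sexual activity | 4 weeks |
| Annex 6, FSFI-6 | 6 (pain on penetration) | Yes, code 0 for no attempt at intercourse | 4 weeks |
| Annex 2, Symptom Questionnaire | 6, 7 | No | None stated |

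Only Annex 2 merges the two groups.

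**Step 2. Size if all women without intercourse follow the instruction.** Inputs:
- N = 230 valid tests (Population and Study Location).
- s, the share without intercourse: not in the protocol; assumed 20%, 30%, 40%.
- p, the frequency of the symptom among women with intercourse: assumed 60%.
- m, the mean item score among women with intercourse on the 1 to 4 scale: assumed 2.5.

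Formulas:
- Recorded frequency = p × (1 − s)
- Recorded item mean = 1 + (m − 1) × (1 − s)
- Ambiguous records = N × s
- Women with intercourse = N × (1 − s)

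| s | Recorded frequency | Recorded mean | Ambiguous records | Women with intercourse |
|---|---|---|---|---|
| 20% | 0.60 × 0.80 = 48% | 1 + 1.5 × 0.80 = 2.20 | 46 | 184 |
| 30% | 0.60 × 0.70 = 42% | 1 + 1.5 × 0.70 = 2.05 | 69 | 161 |
| 40% | 0.60 × 0.60 = 36% | 1 + 1.5 × 0.60 = 1.90 | 92 | 138 |

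The relative loss in frequency is (p − p(1 − s)) / p = s, whatever p is.

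**Step 3. Size if some of them report the symptom anyway.** Let r be the share of women without intercourse who mark some discomfort, for example from memory. Recorded frequency = p(1 − s) + r × s. This is below p whenever r is below p, and equals p when r = p. So understatement does not require r = 0, only that women without intercourse mark discomfort less often than women with it. The instruction makes that likely but does not guarantee it.

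**Step 4. After separation.** With the no-discomfort answers of women without intercourse set aside, and the analysis restricted to women with intercourse, the items return p and m undiluted, over the denominators in the last column of the table.

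**The case against.** The strongest reply has four parts.

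*The information is not lost.* Women without intercourse can be identified from FSFI-6 item 6, DIVA Part C and Annex 3 item 16, and denominators are usually left to an analysis plan, which is not shown here. This stands as far as repair is concerned. It does not remove the ambiguity that the form itself fixes.

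*The all-participant frequency is a legitimate quantity.* The objective refers to the study participants, and among all of them current pain with intercourse is properly rarer when some have none. This stands: 42% against 60% is not in itself bias, because the two figures answer different questions. What is missing is the means to tell which one has been reported.

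*The link to analysis is inferred.* The protocol gives Annex 2 a screening role and plans neither a symptom total nor a correlation of symptoms with DIVA. The named comparators are EQ-5D and FSFI-6, and FSFI-6 item 6 measures the frequency of pain without this ambiguity. This stands. A reader might infer that the validation of DIVA is compromised; nothing in the protocol supports that.

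*Behaviour is assumed.* A reader might infer that every woman who gave up intercourse because of pain is recorded as pain-free, and that the downward bias is therefore certain. The documents do not show this. No recall period is stated, and such a woman may consider that she has the complaint and mark it. Likewise, a reader might infer that women with pain on intercourse as their only symptom are lost at screening. That is possible, but nothing shows that it happens, or how often.

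**Conclusion.** The point holds in a limited form. On items 6 and 7 the printed form allows absence of intercourse and absence of the symptom to share one code, while the other forms with sexual items separate them. Read as severity among women exposed to intercourse, discomfort on these two items is probably understated.

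The size cannot be fixed from the protocol. The range of 48% down to 36% in place of 60% rests on three assumptions: the 60%, a share without intercourse of 20% to 40%, and all such women marking no discomfort. If some report the symptom from past experience, the gap is smaller, and it closes if they do so as often as women with intercourse. The problem is confined to two of seven items, leaves the DIVA items untouched, and is largely repairable from data already collected. What cannot be recovered is the discomfort of women who abstain because of pain and marked none. It is worth correcting because the remedy is cheap and makes the symptom results interpretable.

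**What to change.** **Form, for any further use.** Add a separate answer to items 6 and 7 for no intercourse in the period, and state the recall period, for example the 4 weeks already used in DIVA and FSFI-6. Items 4 and 5 can stay as they are.

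**Forms already completed.** The protocol dates participation from October 2022 to January 2024, so this may be the only part still available.
- Identify women without intercourse from code 0 on FSFI-6 item 6, with Annex 3 item 16 as a cross-check. Item 16 should not lead, because it asks about sexual activity, and DIVA counts self-stimulation as such.
- For these women, treat only a no-discomfort answer on items 6 and 7 as not assessed. Keep any discomfort they did report; blanket recoding would erase real symptoms, possibly the one that qualified a woman for the study.

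**Reporting.** Give both symptoms among women with intercourse, next to the all-participant figure and the number not assessed. Leave not-assessed items out of any symptom total.

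**Cost.** One tick box on two items, a recall statement and one recoding rule. The denominator for the two items falls, for example from 230 to 161 at an assumed 30% without intercourse. At a frequency of 60%, the 95% half-width then rises from 1.96 × √(0.24/230) = 6.3 to 1.96 × √(0.24/161) = 7.6 percentage points. Because FSFI-6 covers 4 weeks and Annex 2 no stated period, a few women with intercourse shortly before that window will be set to not assessed.

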### **Symptom Classification:**

- 1 - No Discomfort
- 2 - Mild Discomfort
- 3 - Moderate Discomfort
- 4 - Intense Discomfort

---

#### **1. Vaginal or Vulvar Dryness**

- 1 No Discomfort
- 2 Mild Discomfort
- 3 Moderate Discomfort
- 4 Intense Discomfort

#### **2. Vaginal or Vulvar Irritation**

- 1 No Discomfort
- 2 Mild Discomfort
- 3 Moderate Discomfort
- 4 Intense Discomfort

#### **3. Vaginal or Vulvar Itching**

- 1 No Discomfort
- 2 Mild Discomfort
- 3 Moderate Discomfort
- 4 Intense Discomfort

#### **4. Vaginal or Vulvar Burning or After Sexual Intercourse**

- 1 No Discomfort
- 2 Mild Discomfort
- 3 Moderate Discomfort
- 4 Intense Discomfort

#### **5. Vulvar or Vaginal Discomfort or After Sexual Intercourse**

- 1 No Discomfort
- 2 Mild Discomfort
- 3 Moderate Discomfort
- 4 Intense Discomfort

#### **6. Pain During Sexual Intercourse**

- 1 No Discomfort
- 2 Mild Discomfort
- 3 Moderate Discomfort
- 4 Intense Discomfort

#### **7. Bleeding or Unpleasant Odor During or After Sexual Intercourse**

- 1 No Discomfort

- 2 Mild Discomfort
- 3 Moderate Discomfort
- 4 Intense Discomfort

---

**Of these 7 symptoms, the one that bothers you the most or disturbs your life the most is:**

### **Annex 3: Sociodemographic and Clinical Questionnaire**

**Questionnaire:** \_\_\_\_\_

**Age:** \_\_\_\_\_ years **Height:** \_\_\_\_\_ cm **Weight:** \_\_\_\_\_ kg

**1. Ethnicity:**

- White (European, Hispanic, North African, Middle Eastern)
- Black (African, Caribbean, African American)
- South Asian (Indian, Pakistani, Bangladeshi)
- East Asian (Chinese, Japanese, Korean)
- Other

**2. Marital Status:**

- Single
- Cohabiting
- Married
- Divorced
- Widowed

**3. Education Level:**

- Up to 4th grade
- 5th to 9th grade
- 10th to 12th grade
- Bachelor's degree
- Master's/Doctorate

**4. Employment Status:**

- Employed
- Retired
- Unemployed

**5. Current Occupation (or previous occupation if retired):**

- Executive/Manager
- Specialist in intellectual and scientific professions
- Technicians and intermediate-level professionals
- Administrative and similar staff
- Service personnel and salespeople

- Industrial workers, agriculture, cleaning

6. **Profession:** \_\_\_\_\_

7. **Do you smoke?**

- Yes
- No

8. **Do you drink wine weekly (more than 3 glasses)?**

- Yes
- No

9. **Type of residence:**

- Owned
- Rented
- Shared
- Apartment
- House
- Nursing home

10. **Menopausal status:**

- Perimenopausal
- Don't know
- Postmenopausal

**Age of menopause:** \_\_\_\_\_ years

11. **Ner of pregnancies:** \_\_\_\_\_ **Ner of vaginal births:** \_\_\_\_\_ **Ner of caesarean sections:** \_\_\_\_\_

12. **Gynecological surgeries:**

- No
- Yes

**If yes, which ones:** \_\_\_\_\_

13. **Hormonal treatments (creams or vaginal suppositories):**

- No
- Yes

**If yes, which one:** \_\_\_\_\_

14. **Do you use vaginal lubricants?**

- No
- Yes

**Do you use vaginal moisturizers?**

- No
- Yes

**14. Contraceptive treatments (pills, patches, implants, devices):**

- No
- Yes

**15. Hormonal treatment for menopause:**

- No
- Yes

**If yes, which one:** \_\_\_\_\_

**16. Current sexual activity:**

- Yes
- No

**Number of years without intercourse:** \_\_\_\_\_

**17. Do you leak urine when coughing?**

- No
- Yes

**18. Do you feel that the walls of your vagina are prolapsed or loose?**

- No
- Yes

**19. Do you have diabetes?**

- No
- Yes

**Do you take medication for diabetes?**

- Yes
- No

**20. Do you have high blood pressure?**

- No
- Yes

**Do you take medication for high blood pressure?**

- Yes

- No

**21. Do you have difficulty sleeping?**

- No

- Yes

**Do you have anxiety?**

- No

- Yes

**22. Have you had cancer?**

- No

- Yes

**If yes, where:** \_\_\_\_\_

**23. Have you undergone chemotherapy/radiotherapy?**

- No

- Yes

## Annex 4 – DIVA English Version

### The Day-to-Day Impact of Vaginal Aging Questionnaire

We are interested in understanding the impact of vaginal symptoms such as vaginal dryness, soreness, irritation, and itching on your day-to-day life. For each question below, please check the answer that best describes how your activities, relationships, and feelings have been affected by any of these symptoms during the past four weeks.

**PART A.** During the past four weeks, how much have vaginal symptoms such as dryness, soreness, irritation, or itching made it uncomfortable or interfered with your ability to:

1. Walk at your usual speed?

 0	 1	 2	 3	 4
Not at all	A little bit	Moderately	Quite a bit	Extremely

2. Wear the clothing or underwear you want?

 0	 1	 2	 3	 4
Not at all	A little bit	Moderately	Quite a bit	Extremely

3. Use the toilet or wipe yourself after using the toilet?

 0	 1	 2	 3	 4
Not at all	A little bit	Moderately	Quite a bit	Extremely

4. Sit for more than an hour?

 0	 1	 2	 3	 4
Not at all	A little bit	Moderately	Quite a bit	Extremely

5. Get a good night's sleep?

 0	 1	 2	 3	 4
Not at all	A little bit	Moderately	Quite a bit	Extremely

**PART B.** During the past four weeks, how often have vaginal symptoms such as dryness, soreness, irritation, or itching caused you to feel:

6. Depressed or down?

 0	 1	 2	 3	 4
Never	Rarely	Sometimes	Fairly often	Very often

7. Embarrassed?

 0	 1	 2	 3	 4
Never	Rarely	Sometimes	Fairly often	Very often

8. Frustrated or resentful?

 0	 1	 2	 3	 4
Never	Rarely	Sometimes	Fairly often	Very often

9. Bad about yourself?

 0	 1	 2	 3	 4
Never	Rarely	Sometimes	Fairly often	Very often

**PART C.** The following questions ask about the impact of your symptoms on vaginal sexual intercourse as well as other types of sexual activity such as self-stimulation or masturbation. During the past four weeks, have vaginal symptoms such as dryness, soreness, irritation, or itching affected:

10. Your desire or interest in having sexual intercourse or other types of sexual activity (including self-stimulation or masturbation)?

0      1      2      3      4  
Not at all      A little bit      Moderately      Quite a bit      Extremely

11. How frequently you had sexual intercourse or other types of sexual activity (including self-stimulation or masturbation)?

0      1      2      3      4  
Not at all      A little bit      Moderately      Quite a bit      Extremely

12. Your ability to become aroused during sexual activity (including self-stimulation or masturbation)?

0      1      2      3      4  
Not at all      A little bit      Moderately      Quite a bit      Extremely

Not applicable – I have not had sexual activity of any kind recently

13. Your ability to be spontaneous about sexual activity (including self-stimulation and masturbation)?

0      1      2      3      4  
Not at all      A little bit      Moderately      Quite a bit      Extremely

Not applicable – I have not had sexual activity of any kind recently

15. The amount of pleasure you experienced during sexual activity (including self-stimulation or masturbation)?

0      1      2      3      4  
Not at all      A little bit      Moderately      Quite a bit      Extremely

Not applicable – I have not had sexual activity of any kind recently

16. Your desire or interest in being in a sexual relationship?

0      1      2      3      4  
Not at all      A little bit      Moderately      Quite a bit      Extremely

17. Your confidence that you could sexually satisfy a partner?

0      1      2      3      4  
Not at all      A little bit      Moderately      Quite a bit      Extremely

18. Your overall satisfaction with your sex life?

0      1      2      3      4  
Not at all      A little bit      Moderately      Quite a bit      Extremely

**PART D.** The following statements describe ways in which your vaginal symptoms may have affected your feelings about yourself and your body. Please indicate how true each of the following statements has been for you during the past four weeks.

19. My vaginal symptoms make me feel like I'm getting old.

0      1      2      3      4  
Not at all true      A little true      Somewhat true      Mostly true      Definitely true

20. I feel undesirable because of my vaginal symptoms.

 0	 1	 2	 3	 4
Not at all true	A little true	Somewhat true	Mostly true	Definitely true

21. When I think about my vaginal symptoms, I feel like I have lost something.

 0	 1	 2	 3	 4
Not at all true	A little true	Somewhat true	Mostly true	Definitely true

22. My vaginal symptoms make me feel like my body is deteriorating.

 0	 1	 2	 3	 4
Not at all true	A little true	Somewhat true	Mostly true	Definitely true

22. I feel less sexy because of my vaginal symptoms.

 0	 1	 2	 3	 4
Not at all true	A little true	Somewhat true	Mostly true	Definitely true

Thank you!

---

#### **Recommended scoring**

Total scores for each domain scale are computed by calculating the average of scores for the corresponding individual items. The possible score range for all domain scales is 0 to 4, with higher scores denoting greater impact of vaginal symptoms.

Two versions of the sexual functioning scale are available: 1) a short, 5-item version that can be administered to all postmenopausal women, regardless of sexual activity status; and 2) a longer, 9-item version that includes 4 additional items (12, 13, 14, and 15) that are only appropriate for women with a history of recent sexual activity.

Activities of daily living domain: items 1, 2, 3, 4, 5

Emotional well-being domain: items 6, 7, 8, 9

Sexual functioning domain (short version): items 10, 11, 12, 16, 17, 18

Sexual functioning domain (longer version): items 10, 11, 12, 13, 14, 15, 16, 17, 18, Self-concept and body image domain: items 19, 20, 21, 22, 23

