The DIVA questionnaire analyses and quantifies the impact of female genital aging. It consists of 23 items grouped into 4 constructs, which include the dimensions of daily activities, emotional well-being, sexual function, and self-esteem and body image. There are two versions of the questionnaire: the full version with 23 items, which includes 4 items on sexual function that can only be evaluated in sexually active women, and a shorter version with 19 items that can be applied regardless of sexual activity. Each item is rated on a 5-point Likert scale, with the dimension value obtained by calculating the average of the corresponding items. Higher values indicate a greater adverse impact of atrophy symptoms.

---

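### The DIVA scoring key lists six items, including item 12, for a short sexual-functioning scale that the same section defines as five items without it

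*Protocol*

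**What the plan says.** The Recommended scoring section of Annex 4 describes two versions of the sexual-functioning scale. The first is "a short, 5-item version that can be administered to all postmenopausal women, regardless of sexual activity status". The second is a nine-item version that "includes 4 additional items (12, 13, 14, and 15) that are only appropriate for women with a history of recent sexual activity". The key below these definitions reads "Sexual functioning domain (short version): items 10, 11, 12, 16, 17, 18", and lists items 10 to 18 for the longer version.

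The section also gives the scoring rule: "Total scores for each domain scale are computed by calculating the average of scores for the corresponding individual items".

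Project Rationale, in the protocol body, agrees with the definitions. The full questionnaire has 23 items, including "4 items on sexual function that can only be evaluated in sexually active women", and there is "a shorter version with 19 items that can be applied regardless of sexual activity". It gives the same averaging rule: "with the dimension value obtained by calculating the average of the corresponding items". It does not list which items belong to which dimension. Annex 4 is the only place with an explicit item list for each domain.

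**The concern.** The definition and the key cannot both be right. Item 12 is first named as one of the four items that suit only women with recent sexual activity. It is then listed in the scale meant for women whatever their sexual activity.

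The study's general objective is to establish the reliability, consistency and validity of this questionnaire, so the make-up of each scale is central. If the short score is built from the printed key, its internal consistency and validity results describe a six-item set and not the defined five-item scale. Women without recent sexual activity raise a further problem. Item 12 asks about arousal during sexual activity, and they may mark it not applicable. Their short score would then be either missing or averaged over a different number of items from everyone else's.

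**Working it through.** **Inputs, all from the protocol**

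- Annex 4, Recommended scoring: short scale stated as 5 items; longer scale stated as 9 items; stated additional items 12, 13, 14, 15.
- Same section, key: short list {10, 11, 12, 16, 17, 18}; longer list {10, ..., 18}; daily living items 1 to 5 (5 items); emotional well-being items 6 to 9 (4 items); self-concept and body image items 19 to 23 (5 items).
- Project Rationale: 23 items in full, 4 of them only for sexually active women, 19 in the short version.

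**Step 1: the stated count.** The printed short list has 6 items against the stated 5, so the figure is not reproduced. Under that list the longer version adds 9 − 6 = 3 items, not the stated 4.

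**Step 2: the set implied by the definition.** {10, ..., 18} minus {12, 13, 14, 15} = {10, 11, 16, 17, 18}, which is 5 items. The only difference from the printed list is item 12.

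**Step 3: questionnaire length** (daily living + emotional + sexual + self-concept).

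| Sexual-functioning items used | Total |
|---|---|
| Longer version | 5 + 4 + 9 + 5 = 23, as stated |
| Short version as printed | 5 + 4 + 6 + 5 = 20, stated 19 |
| Short version without item 12 | 5 + 4 + 5 + 5 = 19, as stated |

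**Step 4: the English form.** In Part C of the Annex 4 questionnaire, item 12 offers a not-applicable response. Items 10, 11, 16, 17 and 18 do not. This matches Step 2.

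**Step 5: effect on a score.** Let m5 be the mean of items 10, 11, 16, 17 and 18, and x12 the answer to item 12. For a woman who answers all six:

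(5·m5 + x12)/6 − m5 = (x12 − m5)/6

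- Item 12 equal to the mean of the others: 0.
- Each point of difference: 1/6 = 0.17.
- Illustration at m5 = 2.4: (0 − 2.4)/6 = −0.40 if x12 = 0, and (4 − 2.4)/6 = +0.27 if x12 = 4.
- Limit: 4/6 = 0.67, reached only if the five core items are all at one end of the scale and item 12 is at the other.

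If item 12 is marked not applicable and the five core items are answered, averaging the answered items gives the defined score exactly. If all six answers are required, the score is missing.

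**Step 6: group mean.** The documents give no item means. Assuming that the mean of item 12 differs from the core-item mean by 0.5 to 1.0 points, the mean short score shifts by 0.5/6 = 0.08 to 1.0/6 = 0.17.

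**The case against.** The strongest case on the other side accepts the contradiction and disputes how much it matters.

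- **The correct set can be recovered on the page.** The definition stands just above the key, and the protocol body agrees with it. Parts A to D of the questionnaire also group the items by domain. This is true of a careful reader, but a scoring program is normally written from the key, and the short-version line is the one that is wrong.
- **The annex reproduces the instrument's own English form, so the slip may come from the source.** The documents cannot show where it arose. Either way, the protocol adopts this key and gives no other.
- **No short score is promised.** The protocol describes both versions and does not say which will be analysed, or which will be compared with the FSFI-6. The consequence is therefore conditional, and no effect on the FSFI-6 comparison is claimed.
- **The size formula covers women who answer item 12.** These are mostly sexually active women, for whom the nine-item version is available. This stands: for the others the result is an unchanged or a missing score, depending on a missing-item rule.
- **The Portuguese form in Annex 1 offers not applicable on all of items 10 to 18.** This also stands. A woman without recent sexual activity may leave the five core items unscored as well, so correcting the key does not by itself secure a short score for her. That is a separate matter and does not make the printed key right.

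**Conclusion.** The concern holds. The short-version line of the scoring key contradicts the definition in its own section and the item counts in Project Rationale. Item 12 is the only item whose removal reconciles all of them.

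The effect is bounded and conditional on a short score being computed from the printed key. For a woman with all six answers it is (x12 − m5)/6, at most 0.67 on the 0 to 4 scale. The group shift of 0.08 to 0.17 rests on an assumed difference in item means. The effect on reliability coefficients cannot be calculated from the documents; the point there is that they would belong to a different scale. The nine-item score and the other three domains are not affected. It should be corrected because the study exists to validate this instrument and the correction is very small.

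**What to change.** Change the short-version line of the key in Annex 4 to items 10, 11, 16, 17 and 18, and keep item 12 in the nine-item version only. Use the same set in any scoring program. Check the line against the original publication of the instrument. If the annex is found to reproduce its source faithfully, report the change as a correction, since the Permissions section asks users to identify modifications.

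The cost is one number in one line, plus a check of any program already written. All 23 items are on the Portuguese form, so the correction discards no collected item and needs no new data. Any short score already computed from the printed key can be recalculated.
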